9.6.2.4 Exploratory objective endpoints

Point estimates and 95% confidence intervals will be derived to determine the rate of hypocalcemia according to PTH levels during the 12 months following cinacalcet initiation.

To explore the kinetics of hypocalcemia, we will plot serum calcium level after first hypocalcemia event according to the treatment intervention employed to manage the hypocalcemia. These will be considered separately by treatment and in combination (i.e. any treatment). Average percentage change in serum calcium from the value at the time of hypocalcemia occurrence will also be summarized.

Point estimates and 95% confidence intervals will be derived to determine the rate of CV events during the 12 months following cinacalcet initiation.

9.6.2.5 Sensitivity Analysis

The analysis for primary endpoints will be repeated by:

- year of KDIGO guidelines introduction (year \leq 2009 vs. $>$ 2009)
- definition of hypocalcemia based on calcium threshold (\leq 8.4 mg/dL) or ICD-10 code of hypocalcemia (E83.51)
- region (Eastern Europe, Western Europe, and Iberian Peninsula)

9.6.2.6 Stratified Analysis

- All primary and secondary analysis will be reported overall for all hypocalcemia patients and stratified by severity: mild (serum calcium \geq 8.0 - $<$ 8.4 mg/dL), moderate (serum calcium \geq 7.5 - $<$ 8.0 mg/dL), severe (serum calcium $<$ 7.5 mg/dL).
- For objective 8.2.4, summary statistics of cinacalcet patients who develop and do not develop hypocalcemia shall be stratified by sex and age.

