8.2 Secondary objectives

HD patients with cinacalcet prescription and serum calcium >8.4 mg/dL at baseline

(Cohort B)

- 8.2.1 To determine the incidence of hypocalcemia in SHPT patients with CKD on HD following cinacalcet initiation
- 8.2.2 To determine the frequency of hypocalcemia events in cinacalcet patients
- 8.2.3 To determine time to first hypocalcemia event
- 8.2.4 To describe characteristics of cinacalcet patients who develop and who do not develop hypocalcemia
- 8.2.5 To identify factors associated with time to hypocalcemia event in cinacalcet patients

Hypocalcemia HD patients who discontinued cinacalcet prescription (Cohort C)

- 8.2.6 To determine time to cinacalcet re-initiation
- 8.2.7 To determine the rate of cinacalcet re-initiation among patients who discontinued cinacalcet following hypocalcemia event
- 8.2.8 To describe factors associated with time to cinacalcet re-initiation event in patients who discontinued cinacalcet following hypocalcemia event
- 8.2.9 To describe treatment patterns (e.g. vitamin D, phosphate binders and CVD medications) at time of hypocalcemia event, at time of discontinuation, and at time of cinacalcet re-initiation
- 8.2.10 To describe the trajectory of PTH, calcium and phosphate values following cinacalcet initiation, following hypocalcemia event, and following cinacalcet re-initiation

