9.2.2 Subject/Patient/Healthcare Professional Eligibility

9.2.2.1 Inclusion/Exclusion Criteria

Inclusion criteria

HD patients in AROii cohort i) aged ≥ 18 , ii) filled a cinacalcet prescription after 01 January 2007, iii) enrolled in AROii for at least 90 days prior to cinacalcet initiation and have at least 90 days follow-up following cinacalcet initiation (*Cohort A*). HD patients who have serum Ca ≥ 8.4 mg/dL at time of cinacalcet initiation will be included in subsequent analyses (*Cohort B*). A sub-set of HD patients who develop hypocalcemia (serum Ca < 8.4 mg/dL) will define *Cohort 1* which will be used to evaluate the primary objectives. HD patients with hypocalcemia who discontinued cinacalcet will be included in further sub-analyses (*Cohort C*).

Exclusion criteria

Patients with i) parathyroidectomy up to and including the first 90 days of follow-up, ii) a prescription for cinacalcet is less than 15 days (2 weeks) with no further prescriptions

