9.2.4.1 Censoring

Patients will begin to accrue time at risk from the end of their relevant baseline period until they experienced hypocalcemia (*Cohort B*), discontinued cinacalcet (*Cohort 1*) or reinitiated cinacalcet (*Cohort C*). Patients will also be censored if they died, underwent parathyroidectomy or a renal transplant, or were lost to follow-up during the respective follow-up periods. Patients will be considered lost to follow-up if they left a dialysis facility for any reason and did not return to the same or another FMC facility within 45 days.

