9.3.2.1 Incidence of hypocalcemia

The cumulative incidence of first hypocalcemia event (# of new cases with serum calcium value <8.4 mg/dL) will be calculated overall and stratified by mutually exclusive groups of mild (≥ 8.0 - < 8.4 mg/dL), moderate (≥ 7.5 - < 8.0 mg/dL), and severe (< 7.5 mg/dL).

The time period will be monthly following cinacalcet initiation. Patients are at risk for each specified time period if they have an active supply of cinacalcet and therefore at risk of hypocalcemia. Patients are not at-risk if they do not have an active supply of cinacalcet, died, had a parathyroidectomy or a renal transplant, or was lost to follow-up during the specified time period.

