9.6.2 Planned Method of Analysis

9.6.2.1 Descriptive Analysis

Baseline characteristics of patients who do vs. do not develop hypocalcemia until end of follow-up of 12 months will be summarized for patients who initiate cinacalcet using descriptive statistics. Summary statistics will be presented for the time-varying covariates of Table 2 for the 90 days prior to initiation, discontinuation and re-initiation for cinacalcet. Continuous variables will be described using the mean and standard deviation, median, 25th and 75th percentiles and minimum and maximum values. Ordinal or skewed variables will be described using a median and range or categorized into meaningful categories at which point categorical data analysis will be applied. Categorical data will be reported as counts and frequencies.

Summary statistics will also be presented for time to first hypocalcemia event, time to any treatment intervention following hypocalcemia event, and time to cinacalcet re-initiation. In addition, cinacalcet prescribing patterns at initiation, at time of hypocalcemia event and after hypocalcemia event and treatment patterns (e.g. vitamin D, phosphate binders and CVD medications) 90 days prior to cinacalcet initiation, at time of cinacalcet initiation, at time of hypocalcemia event, and time of cinacalcet re-initiation will be described. Number of HD patients who initiate cinacalcet with hypocalcemia (<8.4 ng/mL) amongst all cinacalcet users will also be counted.

Plot median and IQR of PTH, calcium and phosphate values every month or quarter during the 12 months following cinacalcet initiation, following hypocalcemia event and following cinacalcet re-initiation. The resulting data will be arranged graphically, stratified by levels of control (Table 3) during the baseline period, to depict the longitudinal pattern of laboratory values following initiation, discontinuation and re-initiation of treatment.

Smoothing techniques may need to be employed to fit the patterns of the laboratory data trajectory.

Table 3. Levels of control

	Serum PTH (pg/mL)	Serum Calcium (mmol/L)	Serum Phosphate (mmol/L)
Low	<150	<2.10	<1.13
Medium	Medium low 150<300	2.10-<2.37	1.13-<1.78
	Medium high 300-<600		
High	≥600	≥2.37	≥1.78

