9.6.2.2 Analysis of the Primary, Secondary and Exploratory Endpoint(s)

9.6.2.3 Primary and secondary objective endpoints

Point estimates and 95% confidence intervals will be derived to determine the rate of hypocalcemia following cinacalcet initiation, rate of cinacalcet discontinuation following hypocalcemia event and rate of cinacalcet re-initiation following discontinuation due to hypocalcemia.

Time to first hypocalcemia event, time to any treatment intervention following hypocalcemia event, and time to cinacalcet re-initiation will be estimated using Kaplan-Meier methods according to baseline calcium levels (i.e. mild, moderate or severe) at baseline.

Cox regression models will be used to identify baseline covariates (Table 2) associated with time to first occurrence of hypocalcemia during the first 12 months of the study, time to any treatment intervention during the 12 months following hypocalcemia event and time to cinacalcet re-initiation during the 12 months following cinacalcet discontinuation. Subjects who do not experience hypocalcemia will be censored (according to 9.2.4.1 criteria). Univariate analysis will be performed. Variables significant at the 0.25 level in univariate analysis will be entered into a multivariate analysis using a stepwise regression technique (significance levels of 0.10 for inclusion/exclusion). Hazard ratios and 95% confidence intervals will be presented.

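### Section 9.6.2.6 stratifies all secondary analyses by hypocalcemia severity without excepting Cohort B objectives 8.2.3 and 8.2.5, where severity exists only after the outcome has occurred

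*Protocol*

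**What the plan says.** Section 9.6.2.6 sets one rule for every primary and secondary analysis: "All primary and secondary analysis will be reported overall for all hypocalcemia patients and stratified by severity". The strata are mild (8.0 to below 8.4 mg/dL), moderate (7.5 to below 8.0) and severe (below 7.5). There is no stratum for 8.4 mg/dL or above.

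The secondary objectives in section 8.2 include two Cohort B time-to-event objectives: "To determine time to first hypocalcemia event" (8.2.3) and "To identify factors associated with time to hypocalcemia event in cinacalcet patients" (8.2.5). Cohort B is defined in section 9.2.2.1: "HD patients who have serum Ca ≥ 8.4 mg/dL at time of cinacalcet initiation will be included in subsequent analyses". Sections 8.2 and 9.2.4 write the bound as strictly above 8.4, but under either version nobody starts below it.

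Other sections keep event-free patients in the analysis. Section 9.2.4.1 on Cohort B: "Patients will begin to accrue time at risk from the end of their relevant baseline period until they experienced hypocalcemia". Section 9.6.2.3 on the Cox models: "Subjects who do not experience hypocalcemia will be censored (according to 9.2.4.1 criteria". Section 9.3.2.1 counts patients with an active cinacalcet supply as at risk in each month.

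Section 9.6.2.3 also groups the Kaplan-Meier curves, including those for time to first hypocalcemia, by baseline calcium labelled mild, moderate or severe.

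**The concern.** In Cohort 1 and Cohort C every patient has already had a hypocalcemia event when follow-up for the objective begins. Severity is then a prior characteristic and a legitimate stratifier. In Cohort B it is a feature of the outcome. A stratum formed from it contains only patients who had the event, so it has no censored members and its curve must fall to zero. A Cox model fitted inside it no longer compares patients who develop hypocalcemia with patients who do not. It asks only how early the event came among those who had it.

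Two results are at stake. The stratified curves would make hypocalcemia look universal and early. The stratified hazard ratios would be pulled toward 1, and the univariate screen and stepwise selection in section 9.6.2.3, if run within strata, could discard real predictors.

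**Working it through.** **The plan's own figure (section 9.5).** Half width = 1.96 × √(0.25/600) = 0.040, as stated. Expected events = 1245 × 0.47 = 585, which the plan rounds to about 600. This figure is not in dispute.

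**Who has a stratum.** On the same planning numbers, 1245 − 585 = 660 patients, or 53%, would have no severity stratum. This carries over to Cohort B only by assumption, because section 9.5 applies 47% to all cinacalcet users.

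**The rules side by side, for 8.2.3 and 8.2.5.**
- 9.2.4.1, 9.3.2.1 and 9.6.2.3: the risk set is all of Cohort B, and event-free patients are censored.
- 9.6.2.6: the reporting population is hypocalcemia patients, split by severity.
- 9.6.2.3, Kaplan-Meier grouping: mild, moderate or severe at baseline. If baseline calcium is the value that qualified the patient for Cohort B, all three groups are empty. They can be filled only with the severity of the later event, which leads back to the same problem.

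**Effect on the curve (illustration).** The assumptions, none of them given by the protocol, are a constant hazard, a proportion p of Cohort B with an event by 12 months, and no other censoring.
- Hazard: h = −ln(1 − p)/12. For p = 0.47, h = 0.0529 per month.
- Full-cohort median: ln 2/h = 0.693/0.0529 = 13.1 months, so not reached within 12.
- Median among event patients: −ln(1 − p/2)/h = −ln(0.765)/0.0529 = 5.1 months.
- Twelve-month incidence: 47% in the full cohort, 100% among event patients by construction.

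Range over p:

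| p | h per month | Median, event patients | Median, full cohort |
|---|---|---|---|
| 0.30 (assumed) | 0.0297 | 5.5 months | 23.3 months |
| 0.47 (section 9.5) | 0.0529 | 5.1 months | 13.1 months |
| 0.50 (section 7.1) | 0.0578 | 5.0 months | 12.0 months |

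The event-only median barely responds to the true risk, which shows how little it says about that risk.

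**Effect on hazard ratios (illustration).** Simulated Cox fits used n = 1245, one binary covariate with 50% prevalence, exponential times, 47% events by 12 months and 60 replicates. The restricted fits pooled all event patients rather than splitting them by severity.

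| True hazard ratio | All patients | Event patients only |
|---|---|---|
| 1.5 | 1.51 | 1.06 |
| 2.0 | 2.00 | 1.12 |

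**The case against.** The strongest reply is that the protocol has a coherent use of severity. Table 1 in section 9.3.2 and section 9.3.2.1 treat it as the type of first event, with cumulative incidence "stratified by mutually exclusive groups of mild", moderate and severe over the at-risk cohort, and section 9.6.1.1 examines incidence in the same way. Section 9.6.2.6 could be read in that light, with the modelling detail left to the SAP. This stands for incidence (8.2.1). It does not settle 8.2.3 and 8.2.5, because 9.6.2.6 names hypocalcemia patients as the reporting population and excepts neither objective. That is a stated rule, not a detail left open, and an SAP that follows it inherits the conflict.

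A reader might infer more than the documents support, in three ways.
- **That time to first hypocalcemia and its predictors would be estimated only in event patients.** They would not: 9.2.4.1, 9.3.2.1 and 9.6.2.3 keep event-free patients in the main analysis.
- **That objective 8.2.4 is also affected.** The second bullet of 9.6.2.6 provides for patients with and without hypocalcemia under that objective, by sex and age.
- **That section 9.6.2.1 asks for event-only summaries.** It says "Summary statistics will also be presented for time to first hypocalcemia event, time to any treatment intervention following hypocalcemia event", without saying how. Since 9.6.2.3 estimates the same times by Kaplan-Meier, the summaries can be censored-data medians and quantiles.

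The objection to the numbers also stands in part. The 47% has no stated time horizon and is not specific to Cohort B.

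**Conclusion.** The point holds for the severity-stratified Kaplan-Meier and Cox analyses of objectives 8.2.3 and 8.2.5. As written, section 9.6.2.6 defines strata by the outcome and conflicts with the protocol's own risk-set and censoring rules. The Kaplan-Meier grouping in 9.6.2.3 has a related fault, since its groups are empty for Cohort B at baseline. The main unstratified analysis is sound if 9.6.2.3 is followed.

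The 100% incidence within each stratum follows from the definition and needs no assumption. The size of the distortion in medians and hazard ratios depends on the constant hazard, the assumed 12-month event proportion, the absence of other censoring and the simulated covariate. It shows direction and rough scale, not a forecast. The wording should be corrected before the stratified analyses are run.

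**What to change.** - **Section 9.6.2.6:** limit severity stratification to Cohort 1 and Cohort C.
- **Objectives 8.2.3 and 8.2.5:** state that the full Cohort B risk set is kept. If results by severity are wanted, analyse mild, moderate and severe first events as event types, with type-specific cumulative incidence and cause-specific hazard ratios. This extends to the time-to-event analyses what Table 1 and section 9.3.2.1 already do for incidence.
- **Section 9.6.2.3:** group the Cohort B Kaplan-Meier curves by baseline calcium categories at or above 8.4 mg/dL.

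The data are retrospective, so the cost is protocol or SAP wording, fewer stratified tables and, if chosen, some type-specific models. The drawback is that severe first events are likely to be few, so intervals for that type will be wide.

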9.6.3 Analysis of Safety Endpoint(s)/Outcome(s)

Safety data will not be collected or analyzed in this study.

9.7 Quality Control

AROii data, comprising detailed patient-level information on medical and drug history, and longitudinal records of biochemical measurements and medications, are provided by FMC to Amgen on a quarterly basis. Fresenius personnel process the data in an initial step (limiting data to the AROii cohort and encrypting patient-identifiable data) but otherwise the data provided are raw. Amgen programmers then undertake an extensive process of data cleaning and quality checking to eliminate double counts, wrongly coded patients, date mismatches and similar discrepancies.

In the final step of the data quality process described above, an 'analysis database' is created. Data are limited to adult chronic haemodialysis patients (defined as ten or more contiguous dialysis treatment sessions) presenting to FMC facilities between 2007 and 2009 and for whom laboratory data were available. Several distinct standardized datasets are created: 1) demographics; 2) laboratory values; 3) transfusion; 4) death; 5) hospitalizations; 6) co-morbidities; 7) medications.

A number of analyses and publications (Anker *et al*, 2016; de Francisco *et al*, 2016; Eckardt *et al*, 2015; Floege *et al*, 2015; Gillespie *et al*, 2015; Stenvinkel *et al*, 2016) have resulted from the standardized AROii dataset.

9.8 Limitations of the Research Methods

9.8.1 Internal Validity of Study Design

9.8.1.1 Measurement Error(s)/Misclassification(s)

In retrospective studies, persistence is often quantified as the number of days of medication available to the patient. This represents a simplified measure, since the definition does not assess if the patient takes the medication (i.e. compliance/adherence). Nonetheless, in the absence of a valid measure and to maintain consistency and comparability between studies of persistence, the number of days the medication was prescribed to the patient during his/her follow-up period is used in this retrospective study.

9.8.1.2 Information Bias

Information bias is unlikely to affect the findings of this study unless investigators record exposures and/or outcomes more diligently for patients treated vs. untreated with cinacalcet. It is possible that hospitalized patients may artificially appear to be non-persistent (i.e. discontinued) as new prescriptions may not be issued until these patients return to FMC. If this is the case then both the time-varying and case cross-over analyses would identify hospitalization as a risk factor, although it should be acknowledged that it would be impossible to determine if this was true (a worsening clinical condition) or artificial effect.

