9.4 Data Sources

An extensive medical record for each haemodialysis patient, essential to their clinical care and encompassing general information, past medical history, physiological anamnesis, comorbidities, allergies, amputations, transfusion history, current medication, laboratory tests, vaccination status, residual renal function, dialysis access, surgery (including parathyroidectomy) and transplantation, is captured directly in the EuCliD system on admission to an FMC facility. These data are reflected in AROii.

Demographic and clinical characteristics include age, gender, height, weight, mobility, marital status, education level, occupational status, smoking history, CKD etiology (coded according to ICD-10) and RRT initiation (country, center, modality and date). Detailed records on patient medical history were used to confirm history of cardiovascular disease, cerebrovascular disease, malignancy and diabetes. Information captured on HD therapy includes dialysis vintage, vascular access type and duration of placement, number of treatments per week, duration of treatment, actual blood flow, dialysis adequacy (Kt/V) as well as pre- and post-dialysis weight. Hospitalization data

including admission and discharge dates and ICD-10 codes, and death data, are routinely captured by all FMC sites.

Descriptive information on prescribed medications includes product (description and ATC code), start and end dates of prescription, dose and administration route. Laboratory data, including markers for anaemia, bone and mineral metabolism, inflammation and nutrition, reflects normal clinical care in terms of testing frequency. Specific to this study, calcium and phosphorous are typically tested on a monthly basis, whilst PTH is tested quarterly.

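### Section 9.8.1.2 judges information bias by a treated-versus-untreated contrast that the study lacks, and leaves open that detection of hypocalcemia depends on how often calcium is tested

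*Protocol*

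**What the plan says.** Protocol section 9.8.1.2 regards information bias as unlikely "unless investigators record exposures and/or outcomes more diligently for patients treated vs. untreated with cinacalcet". It then discusses one other route: hospitalized patients who look as if they had stopped cinacalcet.

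Section 9.2.2.1 admits a patient to Cohort A only if the patient "filled a cinacalcet prescription after 01 January 2007". Cohorts B, 1 and C are nested within Cohort A.

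Hypocalcemia is defined in 9.3.1.2 by a serum calcium below 8.4 mg/dL. Section 9.4 says that laboratory data "reflects normal clinical care in terms of testing frequency", and gives monthly as the usual interval for calcium.

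For incidence, section 9.3.2.1 states: "The time period will be monthly following cinacalcet initiation". It continues: "Patients are at risk for each specified time period if they have an active supply of cinacalcet". The exclusions follow: "Patients are not at-risk if they do not have an active supply of cinacalcet, died, had a parathyroidectomy or a renal transplant", with loss to follow-up as the last. A month without a calcium value is not among them, nor is it among the censoring reasons in 9.2.4.1.

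Section 9.6.2.3 states: "Cox regression models will be used to identify baseline covariates (Table 2) associated with time to first occurrence of hypocalcemia". Table 2 has no term for testing frequency.

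**The concern.** The reassurance in 9.8.1.2 depends on a comparison that no planned analysis makes. The paragraph also refers to case cross-over analyses, which appear nowhere in section 9.6, so it does not seem to have been written for this design.

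The comparisons that are planned set one group of cinacalcet users against another. For these, the relevant question is whether calcium is measured equally often in each group. A month with supply but no test stays in the denominator and cannot produce an event. Extra tests within a month give extra chances of a low value. Either way, a group tested more often has more chances to be classified as hypocalcemic at the same underlying calcium.

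The results exposed are overall incidence (8.2.1), factors associated with time to hypocalcemia (8.2.5) and incidence by PTH level (8.3.2). As the text stands, a report could present these with a statement that information bias is unlikely, for a reason that does not apply.

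**Working it through.** **The plan's own figure.** Section 9.5 expects 47% of about 1245 cinacalcet users to develop hypocalcemia: 1245 × 0.47 = 585, given as about 600. The maximum half width at 600 is 1.96 × √(0.25/600) = 0.040, as stated. This point does not change that figure. The 47% serves below only as a calibration value.

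**Assumptions.** The documents give no testing rates by group. I take 9, 12 and 18 tests a year as a range, with 12 standing for monthly testing. All groups have identical underlying calcium. Whether a test is low follows a probit model with a patient-level random intercept and within-patient correlation 0, 0.3, 0.5 or 0.7. The threshold is set so that the probability of at least one low value in 12 tests is 0.47.

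**Formulas.** P(n) = 1 − E[(1 − pᵢ)ⁿ], where pᵢ is patient i's probability of a low test. The spurious hazard ratio against 12 tests is ln(1 − P(n)) / ln(0.53).

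At correlation 0 this can be done by hand. The per-test probability is 1 − 0.53^(1/12) = 0.0515. Then P(18) = 1 − 0.53^1.5 = 0.614 and P(9) = 1 − 0.53^0.75 = 0.379, giving hazard ratios of 1.50 and 0.75.

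| Correlation | P(9) | P(12) | P(18) | HR, 9 vs 12 | HR, 18 vs 12 |
|---|---|---|---|---|---|
| 0 | 0.379 | 0.470 | 0.614 | 0.75 | 1.50 |
| 0.3 | 0.407 | 0.470 | 0.560 | 0.82 | 1.29 |
| 0.5 | 0.421 | 0.470 | 0.537 | 0.86 | 1.21 |
| 0.7 | 0.435 | 0.470 | 0.517 | 0.90 | 1.15 |

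The two hazard-ratio columns show different mechanisms. The 9-test column concerns untested months. The 18-test column concerns extra tests, where neither group need have an untested month.

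**Second model, untested months only.** Let low calcium begin with probability 0.0515 a month and last 1 to 10 months on average. Each month is tested at random with a fixed probability, and untested months stay in the risk set. The true incidence is 47% throughout. The hazard ratio is against a group tested every month (simulation, 400,000 patients per setting).

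| Months tested | Observed incidence | Apparent HR |
|---|---|---|
| 90% | 43% to 46% | 0.90 to 0.98 |
| 80% | 39% to 46% | 0.79 to 0.96 |
| 50% | 26% to 41% | 0.48 to 0.84 |

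The low end is one-month spells and the high end ten-month spells.

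**Against the selection thresholds.** Section 9.6.2.3 screens at 0.25 and selects at 0.10. Suppose 585 events fall evenly in two groups. The standard error of the log hazard ratio is then about √(4/585) = 0.083. A spurious 1.21 gives z = 0.19/0.083 = 2.3 and would be selected. A spurious 1.15 gives z of about 1.7, near the 0.10 limit. A spurious 0.90 gives z = 0.105/0.083 = 1.3: it passes the screen but not the selection.

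**Would dropping untested months cure it?** In the second model I counted only tested months as at risk. With 80% of months tested, the apparent hazard ratio moves from about 0.8 to about 1.0 for one-month spells. It moves from about 0.9 to about 1.1 for three-month spells, and from about 0.95 to about 1.2 for ten-month spells. A low value that began in an untested month is found at the next test and its event is kept, while the time in which it arose is removed.

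**The case against.** The strongest reply is that the distortion may be small. Section 9.4 gives monthly testing as usual, which matches the monthly period in 9.3.2.1. At 90% of months tested the apparent hazard ratio is only 0.90 to 0.98, and equal testing gives no between-group bias. This stands. A reader might infer that groups tested more often will in fact show more hypocalcemia here, or that patients with high PTH or in certain countries are tested more. The documents do not support that, because they report no testing rates by group.

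Second, the protocol never says in words that untested months are event-free, and 9.8.4 promises an assessment of completeness with imputation or another method. Handling of months without a value could be left to an analysis plan that is not shown. This stands in part. The at-risk rule is nevertheless fixed in the protocol, and 9.8.4 is general and does not mention testing frequency.

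Third, 9.8.1.2 does not dismiss information bias outright, and 9.6.2.1 describes laboratory values after discontinuation, so off-drug periods do appear. Both are true. But the hospitalization remark concerns apparent discontinuation, not detection of low calcium. Off-drug time in Cohort C supplies no untreated comparison group.

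Fourth, the reach is limited. The exposed objectives are secondary or exploratory. The discontinuation rate in Cohort 1, which leads the primary objectives, is not shown to be affected. Country, PTH and dialysate calcium are candidate covariates, so adjustment may absorb part of any testing difference when other factors are estimated. This stands.

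A reader might also infer that the at-risk month should be redefined as one with a calcium value. The last step of the working shows why not: for spells of about three months or longer it reverses the bias instead of removing it.

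**Conclusion.** The point holds in a conditional form. The reason that 9.8.1.2 gives does not address this design, whatever the size of any bias. Detection of hypocalcemia depends on routine testing, and the risk set takes no account of whether a test was done.

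If testing differs between groups, 8.2.5 and 8.3.2 will partly measure testing. If months go untested, 8.2.1 is understated. Under the stated assumptions the spurious hazard ratio is 1.15 to 1.50 for 18 against 12 tests a year and 0.75 to 0.90 for 9 against 12. The values furthest from 1 belong to zero within-patient correlation, those nearest 1 to a correlation of 0.7. Whether such differences in testing exist in AROii cannot be told from the protocol. This merits a correction and a check, and does not invalidate the planned analyses.

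**What to change.** 1. In 9.8.1.2, replace the treated-versus-untreated condition with a statement that detection of hypocalcemia depends on calcium testing frequency among cinacalcet users.
2. Tabulate calcium tests per patient-month, and the share of supplied months with no test, by country and PTH band. This shows whether the issue is material.
3. Keep the 9.3.2.1 risk set for the main analysis. For 8.2.1, 8.2.5 and 8.3.2, add a sensitivity analysis using the first calcium value per patient per month in a discrete-time (complementary log-log) model. Where months are untested, treat onset as interval-censored between consecutive tests. Report it beside the main result.

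Do not redefine the at-risk month as one with a calcium value. Do not require that a factor hold in both models before it is called associated; section 7.3 says that no formal hypothesis is tested, and showing both results is enough.

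The cost is one paragraph of protocol text, one table and one extra model on existing data. Intervals in the sensitivity analysis will be slightly wider, because low values found only on additional tests within a month are set aside. Spells that begin and end between two tests remain undetected under any of these analyses, and the report should say so.
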